#### **3.2. SECONDARY OBJECTIVE**

The secondary objective of the study is to evaluate the safety and tolerability of titration and maintenance therapy with TEV-50717.

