### 5.3. SAFETY ANALYSIS SET

The safety analysis set will include all patients who receive at least 1 dose of IMP. In this population, treatment will be assigned based upon the treatment patients actually receive, regardless of the treatment to which they were randomized. All safety analyses and listings will be based on the safety analysis set.

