### 6.4. VISIT WINDOWS

After mapping the data to the analysis visits of unscheduled and early termination visits, the following rules will apply unless other handling is specified for a particular analysis.

- If there is scheduled visit in the analysis window, scheduled visit will be selected.
- If there is no scheduled visit, but early termination visit, early termination visit will be selected.
- If there are no scheduled or early termination visits, the unscheduled visit will be selected. If there are multiple unscheduled visits, the following rules will be used in sequential order:
  - The record closest to the planned assessment day will be selected for analysis.
  - If there are no scheduled or early termination visits, and 2 records are equidistant from the scheduled day, then the later record will be selected.
- If a patient has no scheduled record or early termination/unscheduled visits in an analysis window, the patient will be considered missing at that visit.

For these analyses performed by time period, e.g. adverse events, the following definitions will be used:

- Titration Period - from the first dose of treatment until the day before the week 7 telephone contact. For patients discontinued before the week 7 telephone contact, the Titration Period is until the later of the last dose of treatment and the early termination visit.

- Maintenance Period - from the day of the week 7 telephone contact until the day of the week 12 visit. If a patient enters the Maintenance Period but discontinues treatment early, the Maintenance Period is until the later of the last dose of treatment and the early termination visit.
- Follow-up Period - from the end of the Maintenance Period through the end of the study.
- Overall Period - includes the Escalation Period, the Maintenance Periods, and the Follow-up Period, if applicable.

If the AE onset date is partial and can be potentially counted in multiple periods, AE will be included with the earliest period.

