For summary tables, patients having more than 1 event with the same PT will be counted once for that term. Patients having more than 1 event with the same SOC will be counted once for each event and once for that SOC. For tabulations by severity, only a patient’s most severe event within the category (e.g. overall, SOC, PT) will be counted; similarly, for tabulations by relationship, only a patient’s most related event within a category will be counted. Summaries will be presented by treatment group and for all patients. The denominator for percentages will be the number of patients in safety analysis set for the given treatment group (i.e., the N’s for the columns).

Summary of all TEAEs will be presented in the overall period (titration plus maintenance phase

plus follow-up period) and for the titration period, maintenance period, and follow-up period. By period summary will be based on the period the AE occurred (Section 6.4). Same type of AE may be counted in multiple periods in cases below:

- AE resolved in the same period and reoccurred in a new period.
- AE increased severity in another period.

Same AE will be counted only once in summary in the overall period.

All adverse events in the overall treatment period will be summarized by CYP2D6 impairment status (Impaired/Not impaired). In addition, serious AEs and AEs by severity will be summarized by CYP2D6 impairment status.

Listings will be provided for all AEs and the following subsets:

- All AEs
- Serious AEs
- AEs leading to study drug discontinuation
- AE leading to dose interruption
- AEs leading to death.

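### The maintenance-period adverse-event percentages use the whole safety set as denominator, so they count patients who left during titration and could not have a maintenance event.

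*SAP*

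**What the plan says.** The secondary objective (SAP 3.2; Protocol 2.2.2) is to "evaluate the safety and tolerability of titration and maintenance therapy with TEV-50717", so maintenance is named in its own right. SAP 9.4 responds with treatment-emergent adverse-event summaries for the overall period and for titration, maintenance and follow-up separately.

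- **Denominator.** SAP 9.4 states: "The denominator for percentages will be the number of patients in safety analysis set for the given treatment group". The sentence applies to the summary tables generally, and no period-specific N follows. SAP 5.3 defines the set: "The safety analysis set will include all patients who receive at least 1 dose of IMP".
- **Periods.** SAP 6.4 starts maintenance on the day of the week 7 telephone contact. For a patient who discontinues before that contact, titration runs to the later of the last dose and the early termination visit. Follow-up starts when maintenance ends.
- **Numerator.** An event belongs to the period in which it occurred. It may be counted in a further period in two cases: "AE resolved in the same period and reoccurred in a new period" and "AE increased severity in another period". On incomplete dates, SAP 6.4 adds: "If the AE onset date is partial and can be potentially counted in multiple periods, AE will be included with the earliest period".

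**The concern.** A percentage in a maintenance table will be read as the risk among patients taking maintenance treatment. Under the stated rule it is not. Patients who left in titration are in the denominator with no chance of being in the numerator, so the figure falls as titration losses rise. If losses differ between arms, the two columns are scaled by different factors, and a difference can appear, shrink or grow for reasons unrelated to what happened in maintenance.

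The numerator adds a separate gap. The dose is raised weekly during titration until there is benefit, a related event of some severity, or the maximum dose (Protocol 3.1.3), so tolerability events may well begin there. One that persists at the same or lower severity into maintenance is not shown in the maintenance table. In the readable text, the by-period summaries are the only adverse-event tables that isolate maintenance, and no exposure-adjusted rate is planned.

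**Working it through.** The SAP gives no figure for these tables, so there is none to reproduce directly. The planned 58 per arm supplies N and a rough bound on dropout.

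**Planned N.** Inputs from Protocol 9.1 are a difference of 6.0, SD 9.5, two-sided 5% and 90% power. Per arm, n = 2 × (1.960 + 1.282)² × (9.5/6.0)² = 52.7, so 53 evaluable (54 with the t distribution). No dropout rate is stated. Reaching 58 implies 1 − 53/58 = 8.6%, or 1 − 54/58 = 6.9%, over the whole study.

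**Denominator effect.** Let N be the safety set of an arm, E the number reaching the week 7 contact, and r the incidence among those E. Then

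reported percentage = r × E/N, and relative understatement = 1 − E/N.

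With N = 58 and whole patients, a 5% titration loss gives E = 55 and a factor of 0.948; 10% gives 52 and 0.897; 15% gives 49 and 0.845; 20% gives 46 and 0.793. At 53 of 58, matching the implied overall dropout, the factor is 0.914.

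**Between arms.** All losses and risks below are assumptions. Differences are in percentage points, active minus placebo, from unrounded values.

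| Titration loss, active / placebo | Entering | True 30% v 30% is reported as | Difference | True 30% v 20% is reported as | Difference |
|---|---|---|---|---|---|
| 5% / 5% | 55 / 55 | 28.4% v 28.4% | 0.0 | 28.4% v 19.0% | 9.5 |
| 10% / 5% | 52 / 55 | 26.9% v 28.4% | −1.6 | 26.9% v 19.0% | 7.9 |
| 15% / 5% | 49 / 55 | 25.3% v 28.4% | −3.1 | 25.3% v 19.0% | 6.4 |
| 20% / 5% | 46 / 55 | 23.8% v 28.4% | −4.7 | 23.8% v 19.0% | 4.8 |
| 5% / 10% | 55 / 52 | 28.4% v 26.9% | +1.6 | 28.4% v 17.9% | 10.5 |

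The last row reverses the losses, and the distortion reverses with them.

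**In counts.** Suppose 9 active and 3 placebo patients leave in titration, and 10 in each arm have a maintenance-onset event. The plan reports 10/58 = 17.2% in both arms. Among entrants it is 10/49 = 20.4% and 10/55 = 18.2%.

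**Persisting events.** Assume 20% of entrants have a new event and titration loss is 10%. The table shows 20% × 0.90 = 18%. If a further 5%, 10% or 20% of entrants have only an unchanged event carried over from titration, then 25%, 30% or 40% of entrants have an event present during maintenance. This gap can exceed the denominator effect. It is limited by the share of entrants who have only such an event, and it compares prevalence with incidence.

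**The case against.** Several points on the other side stand.

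- **Entrants are a selected group.** Restricting to patients who reached week 7 conditions on something treatment may affect. It describes those at risk but is not a cleaner randomised comparison. That is a reason to label the table, not to keep patients with no maintenance period in its denominator.
- **Onset counting is incidence.** SAP 4.5 names incidence of adverse events as the endpoint, so leaving out ongoing events is a defensible choice of measure. This is why the additional row below is optional.
- **Partly recoverable.** SAP 7.1 reports completion of titration and withdrawals by period, so a reader can roughly rebuild the denominator. That does not recover persisting events.
- **Redaction.** The table index cannot be read, so period-specific Ns in the table shells cannot be excluded. The readable rule, however, points to the full safety set.
- **Descriptive tables.** No test is planned. In the count example the difference among entrants is 2.2 points, with a 95% interval of roughly ±15 points, so it does not show that either arm does worse.

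Stronger readings are tempting but not supported:

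- *The rule favours the active drug.* No document forecasts titration loss by arm. Adverse events may be met by dose reduction or suspension (Protocol 5.5), and lack of efficacy is a listed reason for leaving (Protocol 3.11), which could raise placebo losses.
- *The plan expects more than 15% to withdraw.* SAP 7.1 uses 15% as a condition for running a Kaplan-Meier analysis. It is not a forecast, and it covers the whole treatment period.
- *Events count only in their period of onset.* Recurrences and severity increases are counted again.
- *Follow-up has the same fault and the same remedy.* Patients who withdraw early have a safety contact 2 weeks after their last dose (Protocol 4.4), so they may belong in the follow-up denominator. The gap there is that SAP 6.4 gives titration withdrawers no follow-up start.

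**Conclusion.** The point holds for the maintenance table. As written, SAP 9.4 understates maintenance incidence in each arm by the fraction of that arm's safety set that never reached the week 7 contact. If titration loss stays within the roughly 7% to 9% total dropout implied by the sample size, the relative understatement averaged over the arms is under one tenth; at an assumed 15% loss in an arm it is about 15% in that arm. Any distortion between arms needs unequal loss, and its direction cannot be predicted from the documents. The omission of events continuing unchanged or improving from titration is real, but it concerns which measure is reported. The titration and overall tables are correctly based on the full safety set. This deserves correction because maintenance tolerability is a named part of the secondary objective, but it does not undermine the overall safety assessment.

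**What to change.** In SAP 9.4, state that the maintenance-table denominator is the number of safety-set patients in the arm who reached the week 7 contact, and keep the full safety set for the titration and overall tables.

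For follow-up, first add to SAP 6.4 a follow-up start for patients who withdraw in titration. Then use the number entering follow-up on that definition. Applying the present SAP 6.4 definition would wrongly drop withdrawers who are still being followed.

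Optionally, add a supplementary maintenance row per term for events present in the period, whether new or ongoing, labelled as prevalence and kept apart from the incidence rows.

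The cost is SAP wording and one period-entry flag. Event onset and end dates are already recorded (Protocol 7.1.2). Maintenance percentages will look slightly less favourable.

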## 9.5. LABORATORY EVALUATIONS

Laboratory tests will include chemistry panel, hematology panel, and urinalysis testing. Laboratory tests will be performed at the following time points: at the screening visit, and at week 12. If clinically significant laboratory abnormalities have been noticed at week 12 visit, those laboratory evaluations will be repeated at the week 13 visit. A list of laboratory tests is included in Table 4.

Observed values (in SI units) and change from baseline to week 12 will be summarized by treatment group. For hematology and chemistry panel, result will also be categorized as “Normal”, “Low”, or “High” based on their normal ranges. For urinalysis results, tests will be classified as “Normal” or “Abnormal”. Shift tables comparing laboratory test results from baseline to week 12 will be presented.

All laboratory data will be listed. For hematology, chemistry, columns will be included for normal ranges and individual abnormal laboratory values will be flagged. Listing for urinalysis will include the microscopic examination provided for patients who have a positive result from the urinalysis dipstick evaluation.

**Table 4: List of Laboratory Tests**

Serum Chemistry	Hematology	Urinalysis
calcium	hemoglobin	protein
phosphate	hematocrit	glucose
sodium	red blood cell (RBC)	ketones
potassium	count mean cell volume	blood (hemoglobin)
chloride	platelet count	pH
creatinine	white blood cell (WBC) count, and differential count	specific gravity
glucose		microscopic
magnesium	- absolute neutrophil count (ANC)	- bacteria
blood urea nitrogen (BUN)	- polymorphonuclear leukocytes (neutrophils)	- RBCs
total cholesterol	- lymphocytes	- WBCs
uric acid	- eosinophils	- casts
alanine aminotransferase (ALT)	- monocytes	- crystals
aspartate aminotransferase (AST)	- basophils	
lactate dehydrogenase (LDH)		
alkaline phosphatase (ALP)		
bicarbonate or carbon dioxide		
total protein		
albumin		
total bilirubin		
direct bilirubin		

## 9.6. PREGNANCY

Pregnancy tests will be performed for females who are postmenarcheal or  $\geq 12$  years of age. Urine test will be administered at baseline, and serum test will be administered at screening and week 12. The pregnancy data will be presented in a data listing.

## 9.7. URINE DRUG SCREENING

Urine drug screening tests are collected at screening and week 12. The urine drug screening data will be presented in a data listing.

## 9.8. VITAL SIGNS

Vital signs will be measured at screening, baseline, and weeks 2, 4, 6, 9, 12, and 13. Measurements of vital signs will include measurement of pulse, blood pressure (BP), weight, body temperature, and respiratory rate. Pulse and BP in supine or semi-erect/seated position will be measured in each scheduled or unscheduled visits. In addition, standing BP and pulse will be taken at baseline,

weeks 4, and 12. BMI will be computed similarly as in Section 7.2 at week 12 and early termination visits. Weight and height at the visit will be used. Normal age and sex-based z-scores, percentiles for BMI, and BMI categories will also be determined using the WHO growth charts similarly as in Section 7.2.

Orthostatic systolic and diastolic BP and pulse will be calculated as supine or semi-erect/seated measurement – standing measurement. Orthostatic hypotension (determined by blood pressure measurements only) is defined as having either a  $\geq 20$  mmHg reduction from supine to standing position in systolic blood pressure (SBP) or  $\geq 10$  mmHg reduction from supine to standing position in diastolic blood pressure (DBP) or both. Orthostatic tachycardia is defined as pulse increase  $\geq 20$  bpm from supine to standing position.

Observed values, change from baseline, for each vital sign parameter and position will be summarized at each visit by treatment and overall.

In addition, orthostatic hypotension or orthostatic tachycardia occurrences, and the markedly abnormal post-baseline vital signs results will also be summarized for patients with at least one markedly abnormal value during the treatment period according to criteria specified in Table 5. A listing will be provided for all markedly abnormal vital signs. A shift table for BMI age and sex adjusted categories will be presented comparing shifts from the baseline visit to end of treatment. Percentages will be based on the number of safety patients with a non-missing value for both the baseline and post-baseline visit for the given vital sign.

**Table 5: Criteria for Markedly Abnormal Vital Sign Parameters by Age**

Parameter (unit)	Age (years old)	Markedly Low	Markedly High
SBP (supine, standing) (mmHg)	6-12	Value $\leq$ 70 and $\geq$ 20 decrease from baseline	Value $\geq$ 120 and $\geq$ 20 increase from baseline
	13-18	Value $\leq$ 90 and $\geq$ 20 decrease from baseline	Value $\geq$ 135 and $\geq$ 20 increase from baseline
DBP (supine, standing) (mmHg)	6-12	Value $\leq$ 40 and $\geq$ 15 decrease from baseline	Value $\geq$ 80 and $\geq$ 15 increase from baseline
	13-18	Value $\leq$ 50 and $\geq$ 15 decrease from baseline	Value $\geq$ 90 and $\geq$ 15 increase from baseline
Pulse rate (supine, standing) (bpm)	6-10	Value $\leq$ 60 and $\geq$ 15 decrease from baseline	Value $\geq$ 135 and $\geq$ 15 increase from baseline
	11-18	Value $\leq$ 50 and $\geq$ 15 decrease from baseline	Value $\geq$ 120 and $\geq$ 15 increase from baseline
SBP orthostatic criteria (mmHg)	~	$\geq$ 20 decrease from supine to standing position	NA
DBP orthostatic criteria (mmHg)	~	$\geq$ 10 decrease from supine to standing position	NA
Pulse rate orthostatic criteria (bpm)	~	NA	$\geq$ 20 increase from supine to standing position
Temperature (°C)	~	NA	Value $\geq$ 38.3°C and $\geq$ 0.8°C increase from baseline

Note: ~ means that the abnormal range is applicable for all patients within age group: 6 to 17 years old.

Vital signs data will be provided in a data listing.

## 9.9. ECG

Assessment of Standard 12-lead ECG are obtained at screening, baseline, weeks 4, 6, and 12. A central ECG Standard 12-lead ECG will record heart rate (HR), PR interval, RR interval, QT interval, Frederica's corrected QT interval (QTcF), and QRS duration. The overall ECG assessment will be centrally reported as "Normal" or "Abnormal" with respect to relevant abnormalities. If a post-baseline QTcF value  $>500$  msec or change from baseline  $>60$  msec is found, the investigator should repeat the ECG assessment twice. In this case, the confirmed QTcF, defined as the average of all 3 ECG values at the visit, will be used for summary. If ECG tests are repeated on the same day for any other reason per investigators discretion, the average of all ECG values on that day will be used for summary.

Observed results of each ECG parameter and change from baseline will be summarized by treatment and overall, and by visit using descriptive statistics.

In addition, for QTcF, average baseline confirmed QTcF (the average of the screening and Day 1 QTcF), and the change from average baseline will be summarized by treatment and overall, and by visit using descriptive statistics.

QTcF values will be classified as having QTc prolongation according to the following conditions.

QTc Prolongation
Confirmed QTcF $>450$ msec
Confirmed QTcF $>480$ msec
Confirmed QTcF $>500$ msec
Increase from baseline QTcF $\geq 60$ msec
Increase from average baseline confirmed QTcF $\geq 60$ msec
Increase from baseline QTcF $\geq 30$ msec
Increase from average baseline confirmed QTcF $\geq 30$ msec

The number and percentage of patients with QTc prolongation will be summarized by treatment and overall, and by visit.

A shift table comparing the overall ECG assessment from baseline to end of treatment will be presented.

In addition, the abnormal post-baseline ECG results will also be summarized for patients with at least one abnormal value during the treatment period. The summary will be completed by treatment and overall, and age groups (6 - < 8 years, 8 - < 12 years, and 12 - < 16 years), and overall using the age at the time of the individual assessment.

Criteria for abnormal values used in the study are presented in [Table 6](#).

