9.7.2. Safety Analysis

All adverse events will be coded using the Medical Dictionary for Regulatory Activities. Each patient will be counted only once in each preferred term or system organ class category for the analyses of safety. Summaries will be presented for all adverse events, adverse events determined by the investigator to be related to study treatment, serious adverse events, and adverse events causing withdrawal from the study. Summaries will be presented by treatment group and for all patients. Patient listings of serious adverse events and adverse events leading to withdrawal will be presented.

Observed values and changes from baseline in laboratory results and vital signs will be summarized descriptively.

Observed values in ECG parameters will be summarized, and counts and percentages of abnormal findings will be presented. In addition, the number and percentage of patients with on-treatment QTcF values > 450 , > 480 , or > 500 msec and change from baseline > 30 or > 60 msec will be presented.

The use of concomitant medications will be summarized by therapeutic class using descriptive statistics. Concomitant medications will include all medications taken while the patient is treated with IMP.

Observed values in the C-SSRS and observed values and changes from baseline in the CDI-2 (Parent and Self-report versions) will be presented by treatment group for all patients.

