## 6. GENERAL ASPECTS FOR STATISTICAL ANALYSIS

### 6.1. GENERAL METHODS

Statistical methodology and analyses are in accordance with the principles outlined by the ICH E9 guidelines. All statistical analyses will be conducted using SAS statistical software version 9.3 or above.

Tables, listings and figures (TLFs) will be produced in accordance with the principles outlined by the ICH E3 guidelines. For most summary statistics, data will be analyzed by the following treatment groups: TEV-50717; Placebo.

Data summaries will use descriptive statistics (number of patients [n], mean, standard deviation [SD], standard error [SE], median, minimum, and maximum) for continuous variables, and frequency and percentage of patients for categorical and ordinal variables, unless otherwise specified. For continuous variables, if  $n < 5$  then only median, min and max will be presented.

Unless otherwise specified, all statistical tests will be two-tailed using a 0.05 level of significance. All confidence intervals (CIs) will be two sided 95% CIs.

Only visits mapped to scheduled visits will be included in by-visit summaries. All visit assessment data will be included in shift tables and will appear in the patient listings.

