## 9. SAFETY

The safety endpoints for this study are as follows:

- Incidence of adverse events
- Observed values and changes from baseline in vital signs
- Observed values and change from baseline in the Children's Depression Inventory, Second Edition (CDI-2), Parent and Self-report Profiles
- Observed values in the Children's Columbia-Suicide Severity Rating Scale (C-SSRS)
- Observed values in electrocardiogram (ECG) parameters and shifts from screening for clinically significant abnormal findings
- Observed values and changes from screening in clinical laboratory parameters (hematology, chemistry, and urinalysis)

The safety analysis set will be used for all safety analyses. Summaries will be presented by treatment group and for all patients.

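### SAP 9.9 sets out QTcF outliers by visit only and does not carry over the once-per-patient on-treatment count in protocol 9.7.2

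*SAP*

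**What the plan says.** Protocol 9.7.2 (Safety Analysis) plans to present the "number and percentage of patients with on-treatment QTcF values" above 450, 480 or 500 msec, and with increases from baseline of more than 30 or 60 msec. It names no breakdown by visit.

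SAP 9.9 (ECG) lists seven QTc prolongation categories: three thresholds for the confirmed value, and increases of at least 30 and at least 60 msec, each taken from baseline and from the average baseline. It then says: "The number and percentage of patients with QTc prolongation will be summarized by treatment and overall, and by visit". A separate paragraph of 9.9 has abnormal post-baseline ECG results "summarized for patients with at least one abnormal value during the treatment period", with the criteria in Table 6.

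Two general rules decide which records reach a by-visit table. SAP 6.1: "Only visits mapped to scheduled visits will be included in by-visit summaries". SAP 6.4: "If there is scheduled visit in the analysis window, scheduled visit will be selected". Under 6.4 an early-termination record is next in line, and an unscheduled record is used only if the window holds neither.

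The visible part of SAP section 12, on changes from the protocol, names only a new exploratory endpoint.

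**The concern.** The protocol's output answers the question *how many patients ever crossed this threshold on treatment?* A by-visit table answers *how many were above it at week 4, at week 6, at week 12?* The second cannot be converted into the first, because the rows do not show whether the same patients recur.

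This matters more for QTcF than for other ECG parameters. A confirmed value above 500 msec, or a confirmed rise of more than 60 msec, is the protocol's own trigger for stopping study drug (Protocol 4.4, 7.1.7, 7.7). With about 58 patients per arm, outlier counts will be small, and a reader will want the patient total.

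**Working it through.** The documents give no QTcF outlier rate, so there is no stated figure to reproduce. The check is a comparison of texts followed by bounds under assumed rates.

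**1. Is an any-time QTcF count specified anywhere in the visible SAP?**

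- *Overall* in SAP 9.9 does not mean any time on treatment. SAP section 9 opens its safety summaries with "Summaries will be presented by treatment group and for all patients", and 9.9 uses the same treatment-and-overall, by-visit phrasing for descriptive statistics of ECG parameters, where it can only mean arms pooled.
- The treatment-period ECG summary does not cover QTcF. Table 6 has criteria for heart rate, PR and QRS only.
- The ECG shift table covers the overall Normal/Abnormal assessment, not QTcF thresholds.
- The SAP writes patient-level treatment-period summaries for other measures: markedly abnormal vital signs (9.8) and the worst C-SSRS category (9.14).

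No such count for QTcF is written in the visible text.

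**2. How far can a by-visit row lie below any-time incidence?**

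Inputs: three scheduled on-treatment ECGs, at weeks 4, 6 and 12 (SAP 9.9); about 58 patients per arm (Protocol 9.1). Assumptions: an equal per-visit rate p, with the same patients in the denominator at each visit.

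- Same patients at every visit: incidence = p.
- Visits independent: incidence = 1 − (1 − p)³.
- Different patients at every visit: incidence = 3p, the maximum.

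| Assumed p | Same patients | Independent | Different patients |
|---|---|---|---|
| 1% | 1% | 2.97% | 3% |
| 2% | 2% | 5.88% | 6% |
| 5% | 5% | 14.26% | 15% |
| 10% | 10% | 27.1% | 30% |

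For p = 2%, the independent case is 1 − 0.98³ = 0.0588. Visits within a patient are usually correlated: a simulation with a normal latent variable at correlation 0.5 gives 5.1%, and at 0.9 gives 3.4%. In patients per arm, 58 × 0.02 = 1.2 at each visit, against 58 × 0.0588 = 3.4 ever (independent) and 58 × 0.06 = 3.5 at most.

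**3. What happens to an unscheduled ECG?**

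Protocol 3.13.5 allows unscheduled ECGs at the investigator's discretion. Applying SAP 6.4:

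- Window also holds a scheduled record: the unscheduled ECG is not in the by-visit table.
- Window holds an early-termination record but no scheduled one: again it is not in the table.
- Window holds neither: the unscheduled ECG is used. If there are several, the one closest to the planned day is taken.

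The second case can involve the readings of most interest. The early-termination visit includes an ECG (Protocol 3.13.3.2.2) and takes place as soon as possible after the last dose (3.13.4). If an unscheduled ECG prompts withdrawal and both records fall in one window, the later ECG is the one tabulated.

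**4. Do the change categories agree?**

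Protocol 9.7.2 uses >30 and >60 msec; SAP 9.9 uses ≥30 and ≥60 msec. The SAP form can only give equal or higher counts.

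**The case against.** The best defence is that this is a gap in one paragraph of the SAP and not a lost safety signal. Several parts of that defence stand.

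- **A reader might infer that the SAP drops unscheduled ECGs.** It does not do so in general. SAP 6.4 maps them to analysis visits and uses them when nothing else fills the window, and 9.9 averages same-day repeats. Only displaced records are left out, and the window limits are not in the visible text, so the frequency is unknown.
- **A reader might infer that a treatment-stopping value would appear only in a listing.** Protocol 7.1.1 and 7.7 make clinically significant ECG findings, and test abnormalities leading to withdrawal, adverse events. Such a value should therefore reach the adverse event tables in SAP 9.4, including the table of events leading to drug discontinuation. Those tables count each patient once, but they do not report QTcF by threshold.
- **A reader might infer that the count will not be produced.** The SAP's table index is redacted and could contain an any-post-baseline row. What can be said is that the visible analysis text does not call for one.
- **A reader might infer that incidence is understated.** That holds only if someone reads a by-visit row as incidence, which its label does not claim. If the same patients are outliers at each visit, the two figures are equal.
- Protocol 9.7.2 does not say in terms that unscheduled ECGs count. Including them is the natural reading of an on-treatment value, but it is a reading.

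None of this supplies the missing specification. A programmer following 9.9 as written would produce by-visit rows and nothing more for QTcF.

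**Conclusion.** The concern holds as a specification gap. The visible text of SAP 9.9 gives QTcF outliers by visit only, Table 6 omits QTcF, and the patient-level on-treatment count in protocol 9.7.2 is neither carried over nor declared as changed in visible section 12.

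The by-visit percentages are a lower bound on any-time incidence. With three scheduled ECGs, incidence is between 1 and 3 times the per-visit rate, or 2% to 6% for an assumed 2%. This rests on an equal rate and a common denominator across visits. The values of p are illustrations, not document figures, and the independence formula is not the ceiling. Displaced unscheduled ECGs could add to the gap by an amount that the documents do not allow to be estimated.

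The point should be corrected because it restores a safety output that the protocol promises in a paediatric trial. It does not show that any QTcF finding would go unreported.

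**What to change.** In SAP 9.9, for every QTcF threshold and change category, add a once-per-patient row by treatment group: *any post-baseline on-treatment ECG, including unscheduled and early-termination ECGs*. Keep the by-visit rows as supportive.

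In the same edit, reconcile the SAP's ≥30/≥60 msec reporting categories with the protocol's >30/>60 msec, or declare the difference in section 12. This concerns reporting only and leaves the protocol's stopping criteria untouched.

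The cost is a short addition to the SAP and a few table rows from data already collected. The reported percentages may be higher than any single by-visit row.
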